function¹⁹. Insertion of a treatment break did not compromise tumor control. Indeed, 1 year local control for the first 76 patients was 97%, comparable to any other prospective or retrospective report. Patients with very poor liver function (Child Pugh B and even C) were treated safely on trial, suggesting that modifying radiation dose part-way through treatment successfully avoided what would have been severe toxicity. Our initial analysis of the first 20 patients evaluable on the study showed that we need to begin adapting treatment prior to the first 3/5 of radiation delivery. We plan to accrue an additional 40 patients to examine the feasibility of up front individualization in addition to mid treatment adaptation to minimize toxicity and maintain excellent local control. We have demonstrated that patients with good liver function and small tumors (<3.5 cm) have excellent local control and very low rates of toxicity. The current protocol looks at adapting therapy for patients with good liver function (CPA to B7) but larger tumors where more liver parenchyma would receive radiation thereby increasing the risk of toxicity and those with poor liver function (CPB8 and above) who at baseline are at increased risk of liver decompensation post treatment. Our interim analysis has revealed that a combination of albumin and bilirubin, called ALBI, which is an accurate predictor of survival for patients with HCC with liver dysfunction³⁶, is as or more useful than ICG in estimating liver function and predicting future toxicity. Thus, either ICG or ALBI can be used in this trial.

1.1.4.1 Adjusting spatial RT distribution based on regional liver function as assessed by perfusion MRI. This protocol builds on over 25 years of experience with high dose liver RT, and in particular adaptive RT aimed at adjusting the global radiation dose based on a patient's measured sensitivity to treatment. The next leap forward is to use functional imaging to spare highly functional portions of the liver. We have previously demonstrated that dynamic contrast-enhanced (DCE or perfusion) MRI correlates with global liver function as measured by ICG, and that regionally, function declines as a function of delivered radiation dose.²⁹ This and, potentially, other advanced MRI techniques, provides the opportunity to sculpt dose away from high-functioning parts of the liver to improve the safety of treatment.

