8.7 Stopping Rules

[figure not shown]
There are separate stopping rules for efficacy and toxicity. The goal is to stop the trial if there is evidence that the true rate of toxicity (defined in section 8.2) exceeds 10% OR the true rate of local progression within 6 months exceeds 30%. The efficacy rule will be evaluated 6 months after the 10th patient is enrolled. Given expected enrollment of about 1 patient per month, this evaluation will occur when approximately 16 patients have been enrolled. The trial will be stopped if 5 or more of the 10 patients with 6 month follow-up experienced disease-related progression within 6 months of treatment. When the true probability of progression within 6 months is 10, 30 or 50%, the probability of stopping is 1, 15 and 62%, respectively.

The toxicity rule will be evaluated after 15 patients are evaluable for toxicity which will occur 3 months after enrollment of the 15th patient. If 4 or more patients experience unacceptable toxicity, defined as radiation induced liver disease, the trial will be halted. When the true probability of toxicity is 5, 10 or 30%, the probability of stopping is <1, 6 and 70%, respectively.

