11.2 Sample Size and Accrual

This is a pilot trial to gather the data necessary to plan a randomized phase II study with a control group receiving standard therapy. The planned accrual is 80 evaluable patients over two years. An evaluable patient is a patient that has received their complete prescribed treatment (including those whose ICG measurements or ALBI precluded the second phase of treatment and those for whom other toxicity prevented them from receiving a full course of treatment). The high level goal of this trial is to define an individualized and adaptive approach to use of RT in this patient population. Key components of individualizing and adapting treatment are models that relate expected toxicity and tumor control outcomes to RT dose and other patient level characteristics. Part of the reason for the sample size of 80 is to refine these models prior to initiating a randomized trial. For toxicity, our preliminary data suggests that mean liver dose (or some other measure of dose to normal liver), baseline liver function (e.g. CP score) and mid-treatment change in ICGR15 are the most important factors. If our overall event rate for toxicity is about 20%, we expect to have approximately 16 toxicity events which, in combination with some data from similarly treated previous patients, should be sufficient to estimate parameters in a toxicity model with 3 predictors. For tumor control, tumor dose is expected to be the most significant predictor. There will likely be a lower rate of local progression events so that this model may need to have fewer predictors. In addition to further defining statistical models this trial will permit us to estimate rates of toxicity and tumor control that will be key when designing a randomized trial with power to reject a specific null hypothesis.

This treatment will be considered sufficiently promising to initiate a phase II trial if it causes toxicity (increase in CP score of 2 points or more within 6 months of treatment) in no more

than 25% of patients and results in a local control rate (at 1 year) of at least 80%.

We expect to be able to accrue 20 patients per year and thus to complete accrual in approximately 4 years.

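### Each stopping rule is applied once, to the first 10 or first 15 of 80 patients; later patients and, as section 1.1.4 most naturally reads, the current strategy have no numeric trial-level rule

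*Combined protocol and SAP*

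**What the plan says.** Section 8.7 (Stopping Rules) sets a goal of stopping if true toxicity exceeds 10% or true local progression within 6 months exceeds 30%, and then gives two rules.

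- Efficacy, timing: "The efficacy rule will be evaluated 6 months after the 10th patient is enrolled". Boundary: "The trial will be stopped if 5 or more of the 10 patients with 6 month follow-up experienced disease-related progression within 6 months of treatment". Stated properties: "When the true probability of progression within 6 months is 10, 30 or 50%, the probability of stopping is 1, 15 and 62%, respectively".
- Toxicity, timing: "The toxicity rule will be evaluated after 15 patients are evaluable for toxicity which will occur 3 months after enrollment of the 15th patient". Boundary: "If 4 or more patients experience unacceptable toxicity, defined as radiation induced liver disease, the trial will be halted". Stated properties: "When the true probability of toxicity is 5, 10 or 30%, the probability of stopping is <1, 6 and 70%, respectively".

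Section 11.2 gives the size of the trial: "The planned accrual is 80 evaluable patients over two years". (The same section later expects 20 patients a year for about 4 years, and 8.7 assumes about 1 a month. The pace does not alter which patients the rules judge.)

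Section 1.1.4 reports an early finding: "first 20 patients evaluable on the study showed that we need to begin adapting treatment prior to the first 3/5" (that is, before the opening phase of the course). It then plans 40 more patients to study up-front individualization. Sections 5.1.3 and 11.1 describe treatment individualized in this way from the start.

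Section 12 provides quarterly meetings of a study-specific monitoring committee drawn from the study team, and quarterly reports to an independent board. It gives neither body a numeric threshold.

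**The concern.** A rule evaluated once, on the first 10 or 15 of 80 patients, can act only on what those patients show. If an excessive toxicity rate is missed at that look, which is quite possible with 15 patients, nothing prespecified brings the question back. If treatment was also changed after patient 20, the patients judged by the rules received the earlier strategy, and the strategy now under test was never subject to either rule. Section 1.1.4 describes the current population as being at raised risk of toxicity or decompensation, because of larger tumors or poorer liver function. A trial-level check is therefore most useful in the part of the trial that lacks one.

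Each rule also waits for its fixed evaluation point, even when the deciding 4th toxicity or 5th progression has already been observed.

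**Working it through.** **1. Reproduce the plan's figures.** Inputs are the boundaries in 8.7. For one look, P(stop) = P(X ≥ r), with X binomial(n, p).

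| Rule | True rate | Stated | Computed |
|---|---|---|---|
| 5 or more of 10 | 10% | 1% | 0.16% |
| | 30% | 15% | 15.0% |
| | 50% | 62% | 62.3% |
| 4 or more of 15 | 5% | <1% | 0.55% |
| | 10% | 6% | 5.6% |
| | 30% | 70% | 70.3% |

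These agree apart from rounding (0.16% would be better printed as <1%). The stated probabilities are single-look probabilities, so each rule was designed as one evaluation.

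**2. Patients after each look.** Toxicity: 80 − 15 = 65 (81%). Efficacy: 80 − 10 = 70 (88%). Sections 8.7, 11 and 12 contain no later look, restart or continuous boundary.

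**3. Position relative to the change.** The first 10 and first 15 patients both lie within the first 20. If the change followed patient 20 of this trial, neither rule covers any patient treated afterwards. Those number 80 − 20 = 60, or 40 by the figure in 1.1.4. Since 20 + 40 = 60, not 80, the documents do not settle which.

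**4. Miss probabilities of the single looks.** Toxicity, 1 − P(X ≥ 4 of 15):
- 20%: 1 − 0.352 = 0.648
- 25%: 1 − 0.539 = 0.461
- 30%: 1 − 0.703 = 0.297

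Efficacy at 50% progression: 1 − 0.623 = 0.377.

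**5. Acting when the count is reached.** The 4th toxicity falls among the first 15 patients exactly when at least 4 of those 15 have toxicity, so the stopping probabilities do not change. The same holds for the 5th progression among the first 10. At a 30% toxicity rate, given that the rule stops, the 4th event falls on average at patient 10.4 (negative binomial mean given at most 15), ignoring the lag before events are observed.

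**6. What later looks would add (illustration only).** Take cumulative boundaries 4/15, 7/30 and 10/45. By the second look, P(stop) = P(X ≥ 4) + Σ P(X = x)·P(Y ≥ 7 − x) over x = 0 to 3, with X and Y independent binomial(15, p). At p = 0.20:

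0.3518 + 0.2501×0.3518 + 0.2309×0.1642 + 0.1319×0.0611 + 0.0352×0.0181 = 0.486

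The third look extends the same recursion.

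| True rate | 15 only | 15, 30 | 15, 30, 45 |
|---|---|---|---|
| 10% | 5.6% | 6.7% | 7.0% |
| 20% | 35% | 49% | 56% |
| 25% | 54% | 72% | 81% |
| 30% | 70% | 88% | 94% |

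Expected number treated at a 30% rate, counting from the restart:
- 60 patients remaining, now: 15×0.703 + 60×0.297 = 28. With looks at 15, 30 and 45: 15×0.703 + 30×0.173 + 45×0.065 + 60×0.059 = 22.
- 40 patients remaining, now: 15×0.703 + 40×0.297 = 22. With looks at 15 and 30: 15×0.703 + 30×0.173 + 40×0.124 = 21.

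**The case against.** **Later patients are not unprotected.** A reader might infer that 65 patients are treated without safeguards. The documents do not support that. Modelled liver risk is limited to 10% for the first part of treatment (5.1.2.3, 5.1.3) and capped at 25% when the second part is chosen (11.1). Liver function is reassessed mid-course, treatment is held for specified declines (5.2), and an independent board receives quarterly reports. This stands, and it lowers the consequence. But the per-patient limits are model predictions, and 11.2 gives refining those models as part of the reason for 80 patients. None of these measures is a trial-level boundary.

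**The timing of the change is a reading.** The sentence in 1.1.4 about the first 20 patients follows an account of the preceding trial, and 20 + 40 does not give 80. The reference to additional patients makes this trial the more natural meaning, but it is not established. If the preceding trial is meant, the point about the superseded strategy falls; the 65 and 70 patients beyond the looks remain.

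**A 20 to 30% rate may not apply to the counted event.** Section 8.7 counts radiation induced liver disease, which 1.1.3 calls very rare. A reader might take the 30% scenario to predict about 0.30 × 65 = 19 to 20 further toxicities; no section suggests such a rate for this event. At 5% or below, both the present rule and the illustrated looks stop less than 1% of the time, so extra looks would change little.

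**Stricter monitoring could stop a trial performing as planned.** Section 11.2 expects about 20% Child-Pugh toxicity and regards up to 25% as promising. If that event were counted, the illustrated looks at 15, 30 and 45 would stop 56% of the time at 20% and 81% at 25%, and would forfeit some of the roughly 16 events wanted for modelling. This stands in full: the illustrated boundaries should not be adopted for that event.

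**The number of looks in a pilot is a design choice.** Largely so. The restart and acting on the count do not depend on it.

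**Conclusion.** The point holds in this form: each rule is evaluated once, on the first 15 (toxicity) or first 10 (efficacy) patients, leaving 65 and 70 of 80 with no prespecified numeric trial-level rule. On the natural but unconfirmed reading of 1.1.4, no patient under the current strategy (60, or 40) is covered by either rule. The printed stopping probabilities are sound as single-look figures; what is missing is any further look. Against the 10% goal, the toxicity look misses a true 20% rate 65% of the time and a true 30% rate 30% of the time.

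This assumes independent patients with a common event rate, and that the figure missing from 8.7 adds no further rule; the text and the reproduced probabilities give no sign of one. The practical gain from more looks depends on which event is counted and how many patients remain. It ranges from almost nothing for a very rare event to a material gain for one occurring at 20 to 30%. This should be fixed, but ongoing review and the per-patient limits keep it from being critical.

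**What to change.** First confirm whether the first 20 patients in 1.1.4 belong to this trial, and reconcile 20 + 40 with 80. Also reconcile the counted event and threshold in 8.7 (radiation induced liver disease, 10%) with sections 11.2 and 11.3 (Child-Pugh increase of 2 or more, about 20% expected, up to 25% accepted). Then amend 8.7:

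1. Restart both counts at the first patient treated under the current strategy, if the reading of 1.1.4 is confirmed.
2. Trigger each rule as soon as its count is reached: the 4th toxicity within the first 15 patients, or the 5th progression within the first 10. The stated probabilities stay as they are.
3. Add at least one later cumulative toxicity look within the remaining accrual, for example at 30 patients, and at 45 if 60 remain. Derive boundaries for the reconciled event and threshold, and restate the stopping probabilities. The boundaries 4/15, 7/30 and 10/45 illustrate the 10% goal only.

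The cost is one protocol amendment, plus tabulating the counted events for the quarterly reports; section 12 does not list such counts among the topics reviewed. The statistical price is a slightly higher chance of stopping at an acceptable rate: in the illustration, from 5.6% to 6.7% (two looks) or 7.0% (three looks) at a true 10%.

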1.1.3 Avoidance of Radiation Induced Liver Decompensation (Change in CP and ALBI score)

Classically, radiation liver damage was measured with the endpoint of radiation induced liver disease (RILD) based on prior work on whole liver radiation^{20,21}. However, in the modern era with daily imaging and highly conformal radiotherapy, RILD is very rare²². Currently, radiation liver toxicity is more aptly defined by functional liver decompensation in terms of the development of portal hypertension, new onset ascites, and encephalopathy as well as objective lab values. Many groups have published on a change in Child-Pugh score of greater than or equal to 2 and change in the albumin and bilirubin (ALBI score) as more meaningful endpoints²³⁻²⁶. One of the key hypotheses of this trial is that by avoiding functional liver and adapting dose based on liver function, we will minimize these toxic effects. The patients who are at highest risk of decompensation are patients who have poor liver function at baseline. Most patients with HCC present with concurrent cirrhosis which puts them at higher risk of decompensation post radiation. Using spatial functional information as well as direct global measures of liver function e.g. ICG, baseline CP score and ALBI, we hope to deliver a tumoricidal dose without causing toxicity.

1.1.4 Adjusting global RT dose based on liver function as assessed through clearance of Indocyanine Green.

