1.2 Study Agent(s) Background and Associated Known Toxicities

We have over 25 years of experience with liver radiotherapy. As discussed above, change in Child Pugh status and ALBI are the primary toxicity endpoints. Additionally, depending on the tumor location and proximity to normal structures including stomach, small bowel, colon, and right kidney, there is a small risk of GI bleed or renal damage. These are quite rare in our experience, minimize with careful treatment planning and delivery. Indocyanine green is FDA approved and has been in use for 50 years to estimate liver function. In patients without an iodine allergy, it is quite safe. Patients with iodine allergies will be excluded from participation in this study.

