5.1.2 Initial radiotherapy plan

5.1.2.1 CT with or without MRI simulation will be performed in treatment planning position, with appropriate immobilization, as is standard of care.

5.1.2.2 Radiation target volumes. The gross tumor volume (GTV) will be defined on CT or MRI. Appropriate patient-specific margins for motion will be added for patients unable to tolerate breath hold for treatment. No margin will be added for microscopic extent, as per routine clinical practice. A PTV margin will be added as per standard practice, typically 5mm radially and 8mm superiorly and inferiorly.

5.1.2.3 PTV Target Doses. Doses will be prescribed to a peripheral covering isodose covering the PTV, except in cases where this would exceed recommended doses to organs at risk (OARs). In these cases, heterogeneous dose distributions sparing these OARs are expected. The dose per fraction will be determined by the risk of liver damage, which will be fixed at $\leq 10\%$ for the initial 3/5 of treatment. The full treatment plan will be devised at this time in order to account for total normal tissue dose if patients are able to proceed with the entire treatment. The remaining 2/5 of treatment will be determined as per section 11 and potentially reduced based on liver function. Maximum prescribed tumor dose will be 55 Gy in 5 fractions, which we have shown that this dose is adequate for 95% local control at 2 years even for large tumors.

5.1.2.4 OAR Limits. Standard OAR limits in routine clinical practice will be applied and will take priority over target coverage.

5.1.3 Radiation Schedule. The first 3/5 of the treatment plan will be delivered in the initial phase. The dose of radiation will be based on baseline ICG or ALBI, CP score, and functional liver imaging for an NTCP < 10% for a predicted CP score change of greater than or equal to 2. After an approximately 4 week break and re-assessment of liver function with ICG testing or ALBI, the final 2/5 of treatment may be delivered, as per section 11. Patients who have, or would be predicted to have, unacceptable Toxicity (as defined in section 8.6) at the reassessment point will receive no additional therapy at that time.

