8.2 Definitions

8.2.1 Adverse Event

An adverse event (AE) is any untoward medical occurrence in a patient receiving study treatment and which does not necessarily have a causal relationship with this treatment. An AE can be any unfavorable and unintended sign (including an abnormal laboratory finding), symptom, or disease temporally associated with the use of an experimental intervention, whether or not related to the intervention.

- All grade 3 and above AEs will be collected, in addition to any grade ≥ 2 gastritis, hepatic pain, vomiting, and fatigue. The NCI CTCAE v 4.0 will be

utilized to grade AEs and for AE reporting.

- Diagnostic and therapeutic non-invasive and invasive (i.e., surgical) procedures will not be reported as adverse events. However, the medical condition for which the procedure was performed must be reported if it meets the definition of an adverse event unless it is a pre-existing (prior to protocol treatment) condition or a condition entirely unrelated to the study radiotherapy (e.g. cardiac, lung, or bladder procedure).
- Abnormal laboratory values or test results constitute adverse events only if they induce clinical signs or symptoms or require therapy. They are to be captured under the signs, symptoms or diagnoses associated with them.
- When an event recurs after it is resolved, it should be handled as a new AE. However, AEs that occur intermittently can be recorded as one AE.

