8.6 Reporting of Unanticipated Problems

There are types of incidents, experiences and outcomes that occur during the conduct of human subjects research that represent unanticipated problems but are not considered adverse events. For example, some unanticipated problems involve social or economic harm instead of the physical or psychological harm associated with adverse events. In other cases, unanticipated problems place subjects or others at increased risk of harm, but no harm occurs.

Upon becoming aware of any incident, experience, or outcome (not related to an adverse event) that may represent an unanticipated problem, the investigator should assess whether the incident, experience, or outcome represents an unanticipated problem. The incident, experience or outcomes is considered unanticipated if it meets all of the following criteria:

1. Unexpected (in terms of nature, severity, or frequency);
2. Related or possibly related to participation in the research; and
3. Suggests that the research places subjects or others at a greater risk of harm than was previously known or recognized.

If the investigator determines that the incident, experience, or outcome represents an unanticipated problem, the investigator must report it to the IRB within 14 calendar days of the study team becoming aware of the problem.

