11.3 Data Analysis Plans

Primary Aims: The first primary aim is feasibility which is defined as the ability to successfully deliver the full treatment including all adaptations and in particular the perfusion based planning and replanning. In the simplest analyses, feasibility will simply be summarized as the proportion of patients for whom the intended treatment was feasible. The reasons for lack of feasibility for any patients will be investigated individually.

The primary efficacy endpoint is local control, measured as the time to progression of the treated lesion. Patients with no evidence of local progression at the time of data analysis will be censored at the last date on which they were evaluated for local progression. Local progression will be summarized with Kaplan-Meier curves. The estimated rate of local control at 6, 12, 18 and 24 months will be estimated and reported with 95% confidence intervals. Cox regression models will be used to assess the relation between the hazard of local progression and tumor dose and other covariates.

The primary toxicity endpoint is defined as a change in Child Pugh score of greater than or equal to 2 within 6 months of SBRT. Secondary toxicity endpoints include changes in ALBI scores and grade 3 toxicities described in section 8. RILD is a rare but serious side effect that will also be summarized if it occurs. Logistic regression models will be used to estimate the association between baseline (primarily baseline liver function such as CP score and mean liver dose and other dose metrics such as D700) and mid-treatment variables (e.g. change in ICGR15) and the probability of toxicity. We will include interactions between dose and baseline liver function as there is some evidence that patients with worse liver function are more sensitive to radiation than patients with better baseline liver function.

Secondary Aims: The relation between various biomarkers and treatment efficacy will be assessed by including the biomarkers as covariates in Cox regression models for local progression. The relation between biomarkers and toxicity will be assessed in logistic regression models for the binary or ordinal toxicity outcomes and linear regression models for continuous measures of toxicity or liver function such as ICGR15 or ALBI.

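### The section 8.7 toxicity rule counts radiation-induced liver disease, which the plan calls rare and does not define, so its stopping probabilities do not describe protection against the primary Child-Pugh endpoint

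*Combined protocol and SAP*

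**What the plan says.** The combined protocol and SAP uses the word toxicity for different events.

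- **Section 8.7, goal.** The trial should stop on evidence that "the true rate of toxicity (defined in section 8.2) exceeds 10" percent.
- **Section 8.7, rule.** There is one look, once 15 patients are evaluable, placed 3 months after the 15th enrolment. "If 4 or more patients experience unacceptable toxicity, defined as radiation induced liver disease, the trial will be halted". The stated chance of stopping is <1, 6 and 70% at true rates of 5, 10 and 30%.
- **Section 8.2.** It gives general definitions of adverse events, serious adverse events and expectedness, and names neither RILD nor a Child-Pugh rise. Section 8.2.1 adds: "Abnormal laboratory values or test results constitute adverse events only if they induce clinical signs or symptoms or require therapy".
- **RILD elsewhere.** Section 1.1.3 says that "in the modern era with daily imaging and highly conformal radiotherapy, RILD is very rare" and presents Child-Pugh and ALBI changes as more meaningful. Section 11.3 says "RILD is a rare but serious side effect that will also be summarized if it occurs". The text gives no diagnostic criteria and no observation window.
- **Primary toxicity endpoint.** Section 1.2 says that "change in Child Pugh status and ALBI are the primary toxicity endpoints". Section 11.3 defines the primary toxicity endpoint as a Child-Pugh change of 2 or more within 6 months of SBRT. Section 11.2 takes a toxicity rate of about 20% (16 of 80) for planning. It accepts up to 25% when deciding whether a phase II trial follows.

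**The concern.** Someone who reads the 70% in section 8.7 alongside section 11 will take it as the chance of halting the trial when 30% of patients have the toxicity under study. That is true only if every Child-Pugh event is also RILD. The plan separates the two: one is rare, the other is expected in about one patient in five.

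The definition cannot be recovered from the cross-reference. Under 8.2.1, a laboratory-driven Child-Pugh rise without symptoms or therapy would not even be an adverse event. Without criteria or a window for RILD, two people applying the rule to the same 15 patients could count differently.

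At stake is the one numerical safeguard on toxicity across the trial. Patients are enrolled because they have poor liver function or larger tumors (sections 1.1.4 and 3.1.8). The Child-Pugh rate could be well above the accepted 25% without the rule being triggered.

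**Working it through.** **Inputs.** n = 15, boundary 4 or more, rates 5, 10 and 30% (section 8.7). Child-Pugh rates 20% and 25% (section 11.2). Accrual of 12 per year (8.7: about 1 per month), 20 per year or 40 per year (11.2: 20 per year, and 80 in two years). RILD rates and the lag from enrolment to end of RT are assumptions.

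**Formula.** P(stop) = P(X ≥ 4), X ~ Binomial(15, p) = 1 − Σ C(15,k) p^k (1−p)^(15−k) for k = 0 to 3.

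**1. The plan's own figures.** p = 0.05 gives 0.0055; p = 0.10 gives 0.0556; p = 0.30 gives 0.7031. The stated <1, 6 and 70% reproduce. The arithmetic is sound; the question is which event it describes.

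**2. The rule as written, counting RILD (assumed rates).**

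| RILD rate | P(stop) |
|---|---|
| 1% | 0.001% |
| 2% | 0.018% |
| 3% | 0.085% |
| 5% | 0.55% |

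A 50% chance of stopping needs a RILD rate of about 24%, which is hard to call rare.

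**3. If RILD rises with Child-Pugh toxicity.** Suppose RILD is a fixed share of Child-Pugh events, so that p = share × Child-Pugh rate. The shares and the 30% and 40% rates are illustrative.

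| Child-Pugh rate | share 10% | share 25% | share 50% |
|---|---|---|---|
| 30% | 0.085% | 2.2% | 17.7% |
| 40% | 0.25% | 5.6% | 35% |

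**4. The same boundary applied to Child-Pugh events.** p = 0.20 gives 0.352; p = 0.25 gives 0.539. Swapping the event alone would halt the trial 35% of the time at the expected rate and 54% at the accepted rate. The 10% goal lies below both rates, so goal and boundary must be revised with the event.

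**5. Timing.** With s months between enrolments (1, 0.6 or 0.3), patient i has a complete 6-month window at the present look if (15 − i)s + 3 ≥ 6 + lag.

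- Lag 0: 12, 10 and 5 of 15 patients at 12, 20 and 40 per year.
- Lag 3 months: 9, 5 and 0.

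Enrolment at the present look is 15 + 3/s = 18, 20 and 25. If the look waits until the 15th patient completes the window, it is 15 + (6 + lag)/s: 21, 25 and 35 at lag 0, and 24, 30 and 45 at lag 3.

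**The case against.** The strongest reply is that section 8.7 is a separate rule for a more severe event. Nothing outside 8.7 says what the stopping rule must count, and a stopping event may differ from the primary endpoint. A 10% goal fits an event rarer than one expected at 20%. Section 8.2.2 notes that ascites, encephalopathy and GI bleeding belong to the usual course of cirrhosis, and the endpoint in 11.3 requires no attribution. Halting a single-arm pilot on unattributed Child-Pugh rises is therefore debatable. This stands as far as it goes: a RILD rule is a legitimate choice. It does not repair the reference to 8.2, supply criteria or a window for RILD, or give the primary endpoint a numerical rule.

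A reader might infer that Child-Pugh toxicity goes unmonitored. The documents do not support that. There are RT holds (5.2), a 10% NTCP limit (5.1.3), a 25% per-patient cap (11.1), reporting of events at unusual frequency (8.2.2) and quarterly independent DSMB review (12.0). None of these sets a threshold on the Child-Pugh rate across the trial, and the 25% in 11.2 governs the next trial rather than halting this one.

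A reader might also infer that evaluability for toxicity is undefined. Sections 5.2, 7.1.1 and 7.2 do address it; what is missing is the observation window for RILD. A figure in 8.7 is not shown, but the text states the event, boundary, look and probabilities.

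**Conclusion.** The point holds. The goal in 8.7 refers to a section that does not define its toxicity. The rule counts a rare, undefined event, and its probabilities do not carry over to the primary toxicity endpoint. At RILD rates of 1 to 5% the chance of stopping is at most 0.55%. That range is an assumption, but the direction is not: a rare event seldom reaches 4 of 15. The figures by share in step 3 also assume that RILD is a subset of Child-Pugh events.

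It would be wrong to conclude that the stated probabilities are miscalculated, since they reproduce. It would also go too far to call this an indispensable correction. Section 1.1.4 reports an analysis of the first 20 evaluable patients. The text does not make clear whether that is this trial; if it is, the single 15-patient look may already have passed. Together with the other safeguards, this makes it a correction that should be made rather than one on which the trial depends.

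**What to change.** Reconcile section 8.7 with 8.2 and section 11:

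- align the counted event with the primary toxicity endpoint in 11.3;
- reconcile the 10% goal with the 20% and 25% in 11.2;
- time the look so that the counted patients have complete 6-month windows;
- state how patients with missing Child-Pugh data or survival-only follow-up are counted;
- recompute and restate the boundary and its stopping probabilities.

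If a separate RILD rule is intended, label it so, define RILD and its window, and state that its probabilities do not cover Child-Pugh toxicity. If the 20-patient analysis is this trial, the reconciled rule should apply to remaining accrual.

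**Cost.** The work is protocol wording and a recalculation. The laboratory values are already collected, but it would be too optimistic to say that no further data provision is needed. Child-Pugh assessment here also uses the exam for ascites and encephalopathy (6.1.4). Missed visits are not deviations (6.3), and some patients move to survival-only follow-up (5.5, 5.6.6).

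The look comes later. Enrolment before it rises by (3 + lag)/s: 3 to 10 more patients at 12 to 20 per year, or 10 to 20 more at 40 per year, for a lag of 0 to 3 months. A lag near 4 months is possible: about 6 weeks to start, 6 to evaluation and 4 to a repeat test make 16 weeks. It would give about 7, 12 and 23 more at the three accrual rates. A pause also becomes more likely. If the look has passed, this delay does not arise. Labelling a separate RILD rule costs wording only, but by itself leaves the primary endpoint without a numerical rule.

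Two further inconsistencies should be reconciled separately, as this point does not depend on them. Section 5.1.3 refers to 8.6 for unacceptable toxicity, although 8.6 covers unanticipated problems. Section 2.3.1.2 writes a Child-Pugh change >2 where 11.3 has 2 or more.
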